## DATA SAFETY MONITORING PLAN (DSMP)

Complete question 15 **OR** 16 depending on the risk of the study. If your study is submitted as [minimal risk](#) and determined by the HSC to be more than minimal risk you will be asked to complete question 16 during the review process.

**15)** If the research is **no more than [minimal risk](#)**, please describe any provisions in place to ensure the safety of participants and the validity and integrity of data. If safety monitoring will occur a safety monitoring plan may include elements such as: parameters for safety review, the frequency in which safety review will occur, the person(s) responsible for safety review, and the plan (including the person(s) responsible) for reporting adverse events, protocol deviations, or noncompliance to the HSC and others (where applicable). Data monitoring may include the specific elements that will be reviewed (e.g., informed consent documentation, verification of the accuracy of data), the frequency of data monitoring, and the person(s) responsible.

**RESPONSE:** The PI will assess for adverse events as per protocol. OCRO study staff will document any protocol deviation, patient’s non-compliance and report them to HSC per policy.

**16)** If the research is **more than [minimal risk](#)**, a more detailed data and safety monitoring plan is required. Please detail the plan for this study below:

QUESTION	RESPONSE

Please identify the types of monitoring (e.g., centralized, on-site, a mix of both) that will be utilized for this study and the rationale for use (why these practices are appropriate given the nature (e.g., multisite) and risk of the study):  If a multisite study and centralized monitoring practices will be employed, describe how processes and expectations for site record keeping, data entry, and reporting will be communicated (e.g., through a Manual of Operations and/or SOP’s):
	N/A

Which individual(s) or group will be responsible for data and safety monitoring (e.g., PI, specific members of the study team, independent monitor(s), DSMB)? Please be specific and indicate who is responsible for what aspects of the study, including what responsibilities are shared:
	N/A

Provide information related to the expertise and qualifications of the individual(s) and/or groups listed above relative to monitoring. Provide a description of any specific training/qualifications required for personnel carrying out monitoring activities including personnel conducting internal
	N/A

 Centralized monitoring means a remote evaluation carried out by study personnel or representatives at a location other than the site(s) at which the clinical investigation is being conducted.

 On-site monitoring means an in-person evaluation carried out by study personnel or representative(s) at the site at which the clinical investigation is being conducted.

data monitoring, statistical monitoring, or other monitoring activities and the presence of scientific and/or clinical knowledge needed to adequately monitor the trial:	
For those who have monitoring responsibilities please describe the plan to provide mentoring, feedback, and additional training to investigators and study staff:	N/A
If this is a multisite study, explain the plans in place to facilitate timely communication of routine monitoring results and immediate reporting of significant monitoring issues to other sites and stakeholders (i.e., CRO, IRB(s)) as well as communication from sites to monitors:	N/A
Please explain how monitoring activities for this study will be documented (i.e., a monitoring log kept in the regulatory binder):	N/A
How are monitoring results communicated to stakeholders (investigator(s), IRB): Please note that the MEE HSC requires that monitoring reports be received within 5 business days of receipt by the MEE PI/study team.	N/A
What processes are in place for addressing unresolved or significant issues (e.g., significant noncompliance with the protocol) identified by monitoring at MEE or across study sites (when applicable):	N/A
If applicable, describe the composition of the Data and Safety Monitoring Board (DSMB) including each member's relevant expertise, experience in clinical research and in serving on other DSMB's and the absence of serious conflicts of interest. Explain if any of the members have relationships with those sponsoring, organizing, conducting or regulating the trial and the nature of these relationships or if the members have no involvement in the design and conduct of the study:  Note whether or not a DSMB is required (e.g., by the funding agency):  Note whether or not a DSMB Charter exists for this study and include it as an appendices or indicate if it will be submitted separately to the HSC at a later date (if for example, the charter will be developed by the DSMB at the initial meeting):	N/A

Address the process for communication of Data and Safety Monitoring Board determinations to the investigator and to the HSC:	N/A
If applicable, please describe the electronic data capture systems you will be using and what training will be provided for those who will be using these systems:	N/A
Include specific data elements (e.g., review of informed consent documentation, confirmation of subject eligibility) that will be reviewed:	N/A
Specify the frequency of data monitoring (a specific number of times, at defined time points, after a certain number of subjects have been recruited or as needed):	N/A
Who will be responsible for data review (e.g., PI, study staff, DSMB)? If this is a shared responsibility indicate which specific elements each person or group is responsible for:	N/A
Specify the parameters (i.e., procedures, laboratory tests, or other measures) that will be used to evaluate the safety of the study treatment(s) or interventions; to include the methods and timing for assessing, recording, and analyzing these parameters:	N/A
Specify the frequency of safety observation (a number of times, at defined time points, after a certain number of subjects have been recruited or as needed):	N/A
Explain who will be responsible for safety review (e.g., PI, DSMB, monitor):	N/A
Address any “stopping rules” for individual research subjects including who will be responsible for making these determinations:	N/A
Address any “stopping rules” for parts of the study, or for the entire study including who will be responsible for making these determinations:	N/A
Address the frequency and process for eliciting adverse event information from research subjects:	N/A
Please acknowledge that adverse events and unanticipated problems will be reported to the HSC in accordance with the HSC policy on Reporting Adverse Events and Unanticipated Problems:	N/A

# Cover Sheet

**Study Title: MUCINEX for Treatment of Filamentary Keratitis**

**NCT No: NCT02859246**

**Date: 7/21/2019**

## Statistical Analysis Performed

[name], et al.

The Ocular Surface 17 (2019) 565–570

[figure not shown]

Fig. 2. Graph showing the number of filaments at baseline and 4 weeks after the addition of oral guaifenesin. (A) Cumulative filament number in all patients who received oral guaifenesin. (B) Separate analysis for patients who only added oral guaifenesin as a new treatment at baseline and patients who received oral guaifenesin and an increase in topical corticosteroids simultaneously.

[figure not shown]

Fig. 3. Graph showing symptoms score (OSDI) at baseline and 4 weeks after the addition of oral guaifenesin. (A) Cumulative OSDI score in all patients who received oral guaifenesin. (B) Separate analysis for patients who only added oral guaifenesin as a new treatment at baseline and patients who received oral guaifenesin and an increase in topical corticosteroids simultaneously.

## Statistical Test of Hypothesis

We calculated the difference in the mean number of filaments and OSDI score between baseline and follow-up visits and evaluated their change over time. We used the paired-sample Wilcoxon signed-rank test if data did not follow a normal distribution and the paired Student t-test in the case of normally distributed data. For all the analyses we considered the average value of both eyes for all variables with the exception of symptom scores (OSDI), which were considered per patient. Data are presented as the mean  $\pm$  standard deviation (SD), a range for continuous variables, and percentages for categorical variables. A twotail P value of less than 0.05 was considered statistically significant in all statistical tests. The statistical analysis was performed using STATA 13.0 (StataCorp, College Station, TX).

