## HYPOTHESES

**4a). Primary Hypothesis** - Hypotheses are more specific than objectives and amenable to statistical evaluation. Your primary hypothesis is your statement of the hypothesized effect on the primary outcome measure. A hypothesis is worded very simply and written as ‘testable’ statements. Your experimental results will prove or disprove your hypothesis. Hypotheses are generally stated in the null form ( $H_0$ ) as they have their basis in inferential statistics. Rejecting the null hypothesis increases our confidence, with a given level of probability, that there is a relationship between the variables being studied. However, a classic scientific hypothesis includes both a null and alternative ( $H_a$ ) hypothesis.

*\*e.g.  $H_0$ : Asthma prevalence rates are not different among children from low and high socioeconomic groups in Istanbul.  $H_a$ : Asthma prevalence rates are different among children from low and high socioeconomic groups in Istanbul.*

**RESPONSE:**  $H_0$ : Oral Mucinex ® does not reduce corneal filaments or symptomatology in patients with filamentary keratitis.  $H_a$ : Oral Mucinex ® twice a day reduces corneal filaments and the symptomatology in patients with filamentary keratitis.

**4b). Secondary Hypotheses** - Although a study is usually based around a primary hypothesis, secondary hypotheses may also be pre-specified although based on outcomes of lesser importance or additional interest. As the primary hypothesis is usually the basis for statistical power calculations, secondary hypotheses with insufficient power will generally not lead to statistically robust conclusions.

**RESPONSE:** N/A

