## STUDY OUTCOMES

**7a). Primary Outcome** - The primary outcome should be the most important and clinically relevant outcome (e.g. clinical, psychological, economic, or other) of the study. This is the measure used to answer your study aim. However, it is also the outcome used to calculate study sample size and power and test the primary research hypothesis. Generally, no more than 1-2 primary outcome measures are pre-specified. Primary outcome measures may be measured in various ways such as: binary (e.g. caesarean/no caesarean, blood loss  $\geq 500$ mL/blood loss  $< 500$ mL); continuous (e.g. weight - kg, blood loss - mL); ordinal (e.g. pain - mild, moderate, severe); time to event (e.g. survival), and counts (e.g. number of infections, number of events occurring).

**RESPONSE:** Reduction of symptoms according to the Ocular Surface Disease Index score after treatment with oral mucinex ® twice a day (total dose is 1.2 g/day) for 4 weeks

**7b). Secondary Outcome(s)** - Secondary outcome(s) are measures of additional or less important research interest. They may include additional clinical, psychological, economic, or safety outcomes (e.g. treatment related side effects/adverse events). However, as these endpoints are not used to calculate study power and sample size it is often not possible to draw robust conclusions from the results.

**RESPONSE:** Reduction in the number of corneal filaments after treatment with oral Mucinex ® twice a day (total dose is 1.2 g/day) for 4 weeks.

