### RESPONSE:

This will be a first-of-its-kind study evaluating an FDA approved and over-the-counter available drug (guaifenesin; Mucinex®) to treat cough as part of the symptoms of common cold. Our study will be the first to evaluate the effect of Mucinex® alleviating the symptoms of filamentary keratitis. No data are available to estimate the changes expected after initiation of Mucinex®. This is a pilot study and represents minimal to no risk to participants, and involves no additional procedures other than the routinely performed clinical assessments. In this pilot study we aim to enroll 15 participants.

**14) Statistical methods** - The statistical methods used for the study objectives/hypotheses (e.g. t-test, chi-squared, multivariate modeling) must be sufficiently detailed. If conducting a randomized controlled study, you should state whether methods will include an “intention to treat” (ITT) analysis, per protocol analysis, or both. An ITT analysis is preferred as it compares all subjects in the groups to which they were originally randomly assigned (despite withdrawal, treatment failure or cross-over). Consultation with a statistician is strongly recommended. [See Harvard Catalyst Statistical Consulting for more information.](#)

**RESPONSE:** We will use a paired T test or a Wilcoxon signed-rank test, depending on the distribution of the data, to assess whether there is a significant difference between pre- and post-therapy symptoms of filamentary keratitis.

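### The SAP applies one unadjusted P<0.05 to OSDI, filaments and possibly two unplanned subsets, without carrying over the protocol's primary/secondary ranking

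*SAP*

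**What the plan says.** **Protocol.** Section 7a gives one primary outcome: "Reduction of symptoms according to the Ocular Surface Disease Index score after treatment with oral mucinex". Section 7b makes the number of corneal filaments secondary. Section 14 plans a paired t-test or Wilcoxon signed-rank test "to assess whether there is a significant difference between pre- and post-therapy symptoms of filamentary keratitis"; it mentions no filament test, no subset and no alpha level. The null hypothesis in 4a, however, covers both outcomes: "Oral Mucinex ® does not reduce corneal filaments or symptomatology in patients with filamentary keratitis". Section 4b answers that there are no secondary hypotheses.

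**SAP.** Statistical Test of Hypothesis treats the two outcomes alike: "We calculated the difference in the mean number of filaments and OSDI score between baseline and follow-up visits". The decision rule is: "A twotail P value of less than 0.05 was considered statistically significant in all statistical tests". No primary test, testing order or adjustment is given, and nothing is labelled descriptive or exploratory.

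The Fig. 2 and Fig. 3 legends show each outcome first in the whole group (for OSDI, "A) Cumulative OSDI score in all patients who received oral guaifenesin") and then by subset: "Separate analysis for patients who only added oral guaifenesin as a new treatment at baseline". The other subset is made up of those whose topical corticosteroids were stepped up at the same time.

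**The concern.** The 5% error rate belongs to a single test. The SAP's rule lets a chance result on the secondary outcome, or in a small subset, carry the same label as the primary result. Hypothesis 4a does not prevent this. Its null is contradicted if either outcome falls, its alternative names both, and neither section 4 nor section 14 says how two results are to be combined.

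The subsets have no basis in the protocol. Section 8 tells patients to keep their current regimen unaltered, so a group with increased corticosteroids was not foreseen. (That section and the legends need reconciling in their own right.) With only 15 participants planned, a significant result in part of the sample is easily over-read.

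**Working it through.** The documents state no family-wise error rate, so there is no figure of theirs to reproduce beyond the 5% per test.

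**Inputs from the documents**
- Two-sided 0.05 per test; paired t or Wilcoxon signed-rank (SAP, Statistical Test of Hypothesis).
- Two outcomes (same section).
- Up to three patient sets: all patients and two separate subsets (SAP, figure legends).
- 15 participants (Protocol 13).

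**Assumptions, because the documents give no values**
- Subset sizes of 8/7, 10/5 and 12/3. Totals of 20 (10/10) and 30 (15/15) were also tried.
- Correlation between the two outcome changes from 0 to 0.9.
- Normally distributed paired changes with no true change in either outcome.

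**Step 1: independent tests.** Chance of at least one false positive among k tests = 1 − 0.95^k.
- k = 1: 5.0%
- k = 2: 1 − 0.9025 = 9.75%
- k = 6: 1 − 0.7351 = 26.5%

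The last figure is too high here. The whole group is the two subsets combined, and the outcomes may be correlated, so the six tests overlap.

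**Step 2: simulation of the actual structure** (100,000 trials per setting).

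| Tests counted | Test | Setting | At least one P<0.05 |
|---|---|---|---|
| OSDI, all patients | t | all settings | 4.9–5.1% |
| OSDI and filaments, all patients | t | correlation 0 to 0.9 | 10% falling to 7% |
| One outcome, three sets | t | all settings | about 12% |
| All six | t | correlation 0 / 0.5 / 0.7 / 0.9 | 22% / 21% / 19–20% / 16–17% |
| All six | exact Wilcoxon, 8/7 | correlation 0 / 0.5 / 0.9 | 20% / 19% / 16% |
| All six | exact Wilcoxon, 10/5 | correlation 0 / 0.5 / 0.9 | 15% / 14% / 11% |

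The first row confirms that a single test returns its nominal 5%. The last row is lower because the smallest two-sided exact Wilcoxon P value with five patients is 2/2^5 = 0.0625, so that subset can never reach 0.05.

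**Step 3: effect of ranking.** If filaments may be called significant only when OSDI is, then with no true change in either outcome a false claim needs a false OSDI result, which has probability 5%. If OSDI truly changes and filaments do not, the false filament claim is still limited to 5%.

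**The case against.** 1. **Subset testing is not shown.** The SAP's methods text describes one comparison per outcome. The subsets appear only in the legends, the figures are not available, and no visible text gives a subset P value. This stands. A reader might infer that six tests were run and the false-positive chance is a flat 20%; the documents do not establish the first, and the second lies within a conditional range. What the methods text itself supports is two whole-group tests, at 7–10%.
2. **Filaments are not new.** A reader might infer from section 14 that the protocol foresaw only a symptom test. But filaments are in the objective, hypothesis 4a, outcome 7b and the data collection plan. Testing them was to be expected; only the subsets are unplanned.
3. **The protocol still ranks OSDI first.** Correct: the SAP is silent on ranking and does not overrule it. Neither document says that any one result suffices. The gap is that the SAP's rule labels every result the same way and 4a supplies no combination rule.
4. **It is an uncontrolled pilot.** Pilot status argues for descriptive reporting, yet the SAP tests hypotheses and declares significance. It is also true that a before–after change can be non-zero without any drug effect. The rates above address chance findings only, and correcting them does not turn a significant change into evidence of efficacy.
5. **The analysis is finished.** A hierarchy devised after the results gives no error control. This stands in part: the OSDI/filament ranking is the protocol's own, but the conditional rule for filaments and the exploratory label are later additions and must be disclosed as such.
6. **The analysis set matters.** Patients for whom guaifenesin was the only new treatment fit section 8's unaltered regimen better than the whole group does. That is a reason to name the set for the OSDI test and to show the subset estimates in full. It is not a reason to leave the choice open.

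**Conclusion.** The point holds as a gap in how results are labelled. The SAP gives both outcomes the same unadjusted threshold without the protocol's ranking, and its legends add two unplanned subsets.

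- If either whole-group result counts as success, the chance of at least one false positive is about 7–10% (t-tests, correlation 0.9 down to 0).
- If both subsets were also tested for both outcomes, it is about 11–22%, depending on assumed subset sizes, correlation and test type.
- The OSDI test in all patients keeps its 5% error.

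A reader might infer that the primary result is compromised; the documents do not support that. The inflation arises only when a filament or subset result is read as a positive finding in its own right. The change should be made because it is cheap and prevents that reading, but it does not bear on the validity of the primary analysis.

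**What to change.** In the SAP, replace the blanket significance sentence with the following:

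- Following protocol 7a and 7b, the paired OSDI change from baseline to follow-up in all treated patients is the single test judged at two-sided 0.05.
- The filament change is secondary. It is called significant only if OSDI is also significant; otherwise its P value is descriptive.
- The Fig. 2B and 3B subset results are exploratory, given as estimates with confidence intervals and not called significant.
- The ranking comes from the protocol; this labelling was added after the analysis was performed.

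The cost is a few sentences and confidence intervals from data already held. The downside is that filament and subset results may lose the significant label.
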